- 4.) the time necessary for return to work in patients between 18 and 60 years?

Trial design

The study design is a parallel group, randomized controlled trial with open allocation including all patients with calcaneus fractures independent of kind of initial therapy.

Methods: Participants, interventions, and outcomes

Study setting

All patients treated for calcaneus fracture (DS920* 'Fraktur af hælben' according to the Danish SKS-browser) at the University Hospital Odense are prospectively screened for eligibility and included in the trial, if they fulfil the inclusion criteria as listed below. The follow-up period is 6 months.

Eligibility criteria

In Denmark, the treatment of calcaneus fractures is regarded as highly specialized, wherefore both decision-making and operations are done for the whole Region of Southern Denmark in the Department of Orthopaedics and Traumatology at the University Hospital Odense. Therefore, patients are screened by consultants of the local trauma section.

Inclusion criteria:

- Fracture of the calcaneus, which is classifiable according to the Sanders' classification (excludes avulsion fractures)
- Being able to understand Danish or English and answer the questionnaires
- Informed consent
- Age between 18 and 65 years

Exclusion criteria:

- Pathological fractures
- Immature skeletal system
- Other fractures with influence on weight-bearing
- A soft-tissue situation not allowing the equipment with a 'Settner shoe' within 3 weeks after treatment (either decision-making for non-operative therapy or open reduction and internal fixation)

Acquiring patient consent

The participants will be introduced to the study by the medical personnel in a room, where they will not be disturbed. It will be assured that patients are allowed (if they wish) to be introduced to the study accompanied by a family member or any other person(s) selected by the patient. Patients will be given an oral overview of the purpose of the study, a participant information document describing the study and potential risk together with a patient consent form, which the patients will sign if they decide to participate in the study. The patient can resign from participating in the study without giving a reason and without any consequences. Patients are included after the operation or after decision for non-operative therapy, but before discharge.

Interventions

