After operation or decision for non-operative therapy, the schedule for the 2 groups are defined as follows:

Group 1 (treatment without 'Settner shoe'):

- mobilization without weight bearing for 6 weeks starting with the day of either decision-making for non-operative therapy or open reduction and internal fixation, if needed a cast or another kind of orthosis as a Static Walker are applied, then 4 weeks 15-20 kg, 2 weeks 35-45 kg, after that transition to full-weight bearing (always only if possible)

- X-ray after 6 and 12 weeks; depending on the results, the schedule for weight bearing may be adjusted to the need in case of delayed healing or complications related to implants

Group 2 (treatment with 'Settner shoe'):

- mobilization with the custom-made heel-unloading orthosis ('Settner shoe') without pads for 6 weeks, then 2 weeks one pad, 2 weeks 2 pads, 2 weeks 3 pads, after that full-weight bearing without any support (always only if possible)
- X-ray after 6 and 12 weeks; depending on the results, the schedule for weight bearing may be adjusted to the need in case of delayed healing or complications related to implants

The patients of both groups are informed about the aftercare at the time point of inclusion.

Outcomes

Primary outcome criterion

The number of active minutes per day following 3 months (time point 2) is primary outcome criterion.

Secondary outcome criteria

- active minutes per day at time point 1
- portion of highly active periods per day at time point 1 and 2
- the EuroQol 5D-3L questionnaire following 3 months (time point 2)

Explorative outcome criteria

- AOFAS
- 3-dimensional gait analysis
- time point of return to work of patients between 18 and 60 years
- range of motion (ROM)
- Pro- and supination (percent of healthy side or assumed normal mobility) are analyzed.
- pain
- The evaluation includes the medication and a visual-analogue scale (VAS).
- comparison between patients with and without operation

Patient characteristics beside outcome criteria

Epidemiology

- age
- sex
- body mass index
- ASA (American Society of Anesthesiologists) physical status classification system

Injury characteristics

- classification according to Sanders (figure 4)
- classification of open/closed tissue damage (table 1)
- polytrauma (ISS \geq 16, multiple injuries, monitrauma)
- indication for operation (dislocation, broadening, flattening of Böhler angle etc.) or conservative therapy (comorbidity, smoking etc.)

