Methods: Data collection, management, and analysis

Management and collection

REDCap™ (Research Electronic Data Capture), a secure application for online surveys and databases, facilitates data management. The University Hospital Odense is an institutional partner of REDCap™, which was especially designed for biomedical research and fulfills all necessary safety features. This is supported by the OPEN initiative (Odense Patient data Explorative Network). REDCap™ used with the OPEN-platform supports also a randomization function, which is used for the study.

Statistical methods

Normally distributed numeric data sets are compared using the paired Student's t-test. Otherwise or in case of non-numeric data, nonparametric tests determine the significance of difference. For correlations, Spearman ρ is calculated. Incidences are compared using the chi square test. Otherwise or in case of non-numeric data, nonparametric tests as the Mann-Whitney U-test for two and the Kruskal-Wallis H-test for multiple variables determine the significance of difference. For correlations, Spearman ρ is calculated.

Methods: Monitoring

Data monitoring

When the study is accepted for OPEN, a data manager will automatically be assigned to the study. The data manager will support the data coherence. Furthermore, a yearly data monitoring will be done by a study nurse, who is assigned to the project.

Harms

Any adverse or severe adverse events will be registered during the trial. Expected are especially local mechanical irritations, which are listed in the chapter for registration of patient characteristics beside outcome criteria.

Ethics and dissemination

Ethics

The study needs to be approved by the ethical board of the Region of Southern Denmark (<https://komite.regionssyddanmark.dk/wm258128>).

Patient law/privacy

All data collected from patients are protected by the Act on Processing of Personal Data and Health Act according to Danish Data Protection Agency. The project will be reported to Datatilsynet (under "Regionens Paraply 2012-58-0018"). The database is established with OPEN, however, other possible related files are stored in a secure Sharepoint (<https://secure.regionssyddanmark.dk/projektrum/ProTibExPla/SitePages/Startside.aspx>).

Publication

Reporting will be conducted according to Consolidated Standards of Reporting Trials (CONSORT guidelines (<http://www.consort-statement.org/>) and published in a peer reviewed journal.

Appendices

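### Time to return to work is cut off at 6 months and by withdrawal, but the plan names no method for censored times and no rule for patients not back at work

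*Combined protocol and SAP*

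**What the plan says.** Research questions, item 4, asks about "the time necessary for return to work in patients between 18 and 60 years". Explorative outcome criteria lists "time point of return to work of patients between 18 and 60 years". The introduction also makes ability to return to work the second part of the hypothesis, and the Orthosis appendix says preliminary data point to fewer days of inability to work.

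Two statements mean that not every return time will be seen. Study setting: "The follow-up period is 6 months". Acquiring patient consent: "The patient can resign from participating in the study without giving a reason and without any consequences".

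Statistical methods sends normally distributed numeric data to a t-test (worded as paired). For other data, "nonparametric tests as the Mann-Whitney U-test for two and the Kruskal-Wallis H-test for multiple variables determine the significance of difference". It adds "Incidences are compared using the chi square test" and Spearman correlation for associations. It names no Kaplan-Meier, log-rank or Cox analysis. It gives no value or rank for a patient not back at work at 6 months, and no rule for a patient lost before then. The documents have no missing-data section.

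Eligibility is wider than this analysis ("Age between 18 and 65 years"), so the return-to-work subset is at most the 25 per group given under Sample size and power analysis. No start point is given for the return time. The control-group schedule does use a natural anchor: "starting with the day of either decision-making for non-operative therapy or open reduction and internal fixation".

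**The concern.** Time to return is a time-to-event quantity. A patient still off work when follow-up ends, or who leaves early, has a return time known only to exceed some value. A t-test or a Mann-Whitney test needs a number or a rank for every patient it includes. If the plan supplies neither, the literal course is to analyse only patients who have a return date.

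That selects on something that happens after randomisation. If the shoe brings more patients back, its returners include slower patients whose counterparts in the control arm are still off work and so are left out. The two groups of returners then look more alike than the randomised groups are. Research question 4 could be answered as no difference when there is one. With several readings open in an open-label trial, the handling could also be chosen after the data are seen.

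**Working it through.** **Plan's own figure.** The plan gives no power, return rate or effect for this outcome. The 25 per group was derived for activity and is used here only as an upper bound on the subset aged 18-60.

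**Readings that the plan leaves open**

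| Reading | Non-returners at 6 months | Lost before 6 months | Uses the time |
|---|---|---|---|
| t-test or Mann-Whitney, returners only | dropped | dropped | yes |
| Mann-Whitney, non-returners ranked last | kept | no rule | yes |
| Chi-square on proportion back | kept | no rule | no |

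Log-rank, which the plan does not name, keeps both groups of patients as censored and uses the time.

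**Assumptions.** Proportion p back at work by 6 months in each arm (assumed); exponential return times, so rate = -ln(1-p)/6 per month; 25 per arm; cut-off 6 months; two-sided 0.05; 4,000 simulated trials per scenario; no earlier loss unless stated. The implied hazard ratio is ln(1-p_shoe)/ln(1-p_control). For 50% v 80% it is 1.609/0.693 = 2.3; for 50% v 70%, 1.204/0.693 = 1.7; for 30% v 60%, 0.916/0.357 = 2.6.

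**Power**

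| Back by 6 months | Log-rank | Ranked last | Chi-square (uncorrected) | Mann-Whitney, returners only |
|---|---|---|---|---|
| 30% v 60% | 0.59 | 0.56 | 0.62 | 0.06 |
| 50% v 70% | 0.32 | 0.29 | 0.33 | 0.07 |
| 50% v 80% | 0.67 | 0.62 | 0.64 | 0.11 |
| 70% v 90% | 0.54 | 0.46 | 0.45 | 0.14 |
| 80% v 96% | 0.63 | 0.53 | 0.44 | 0.24 |
| 90% v 99% | 0.65 | 0.52 | 0.20 | 0.36 |

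At 50% v 80% the returners-only test uses on average 32.5 of 50 patients. An unpaired t-test in returners does little better (0.12 at 50% v 80%, 0.26 at 80% v 96%).

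**Why power falls.** The median in all patients is ln 2/rate; the median in returners is -ln(1-p/2)/rate.
- 50% v 80%: all patients 6.00 - 2.58 = 3.4 months; returners 2.49 - 1.90 = 0.6 months.
- 80% v 96%: all patients 2.58 - 1.29 = 1.3 months; returners 1.90 - 1.22 = 0.7 months.

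At 50% v 80%, (0.624 - 0.108)/(0.674 - 0.108) = 91% of the power lost from log-rank to returners-only comes from dropping non-returners, and the rest from using Mann-Whitney. At 90% v 99% that share is (0.524 - 0.358)/(0.648 - 0.358) = 57%.

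**Cost of ranking last instead of log-rank.** The smallest gap is at 50% v 70%: 0.315 - 0.291 = 0.024. The largest is at 90% v 99% with 15% lost over the 6 months: 0.630 - 0.483 = 0.147. The range is about 0.02 to 0.15.

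**Sensitivity**
- Weibull shape 2 instead of exponential, 50% v 80%: 0.66 / 0.61 / 0.63 / 0.10, in the order of the table.
- 15 per arm, 50% v 80%: 0.46 / 0.41 / 0.42 / 0.08.
- Hazard ratios of 1.3 to 1.5, control return 50-90%, 25 per arm: log-rank about 0.10-0.29, ranked last 0.09-0.25, returners only 0.05-0.15.
- No effect (50%, 80% or 90% back in both arms): returners-only rejects in 0.042-0.047 of trials and log-rank in 0.050-0.052. The highest figure is 0.062, for uncorrected chi-square.

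**The case against.** The strongest reply is that the large loss belongs to one reading that the plan never states. A reader might infer that the plan commits to analysing returners only. It does not: no section says so, Mann-Whitney can take non-returners as tied at the worst rank, and the introduction's wording about ability to return to work fits a chi-square on the proportion back. On those readings the tests already listed do nearly as well as log-rank at low to middle return rates, and chi-square is marginally ahead at 30% v 60% (0.62 v 0.59). This stands, and it limits the size of the point. It does not remove it: the plan does not choose between the readings, none of them deals with loss before 6 months, and chi-square ignores the time that research question 4 asks about.

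The second reply is that the outcome is explorative and the tabulated effects are large. This also stands. Even log-rank misses the effect in roughly a third to two thirds of trials in the table, and with hazard ratios of 1.3 to 1.5 a non-significant result is likely whatever the method. A reader should not infer that log-rank would make research question 4 adequately powered.

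Third, the baseline lists do not mention whether the patient worked before injury. A reader might infer that this is not collected. The case report form is not among the documents, so that cannot be concluded.

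**Conclusion.** The point holds as a gap in the analysis plan for a named research question: return time will be censored, no listed test handles censoring, and no rule covers patients who are not back or are lost. A literal application of the t-test or Mann-Whitney rule would attenuate a real effect. Under the assumed rates, power falls from 0.67 to 0.11 at 50% v 80% and from 0.63 to 0.24 at 80% v 96%. Ranking non-returners last or using chi-square avoids most of that loss at low to middle return rates; at high return rates chi-square falls well behind.

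These sizes rest on assumed return rates, hazard ratios of about 1.7 to 2.6 and at most 25 per arm. The documents supply none of the rates. A reader might infer a risk of a spurious benefit or damage to the main result; neither is supported. Dropping non-returners does not raise the false-positive rate when there is no effect, and the primary outcome, active minutes per day at 3 months, is untouched. Severity: consider.

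**What to change.** Add to Statistical methods, for example:

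> Return to work in patients aged 18-60 is measured from the date of surgery, or of the decision to treat without surgery, to the first return to work. Groups are compared by Kaplan-Meier curves and the log-rank test. Patients not back at work are censored at 6 months or, if earlier, at the last contact at which work status is known. The proportion back at work by 6 months is also reported, with the difference and its 95% confidence interval.

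If the listed tests are to be kept, the minimum is to state that patients not back at 6 months are ranked last. This costs about 0.02 to 0.15 in power against log-rank in these scenarios and leaves earlier loss unresolved.

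The text itself costs a few sentences, with two conditions. Censoring at last contact assumes that loss is non-informative, which is uncertain in an open-label trial and should be stated as a limitation. Work status must also be known up to 6 months. The available text describes assessments at about discharge, 6 weeks and 3 months but no 6-month contact, although a timeline figure may be missing. If none is planned, either add a contact for work status, or censor at the last planned contact and report the proportion back at that time instead.

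Recording whether the patient worked before injury is an optional addition. Restricting the analysis to such patients would shrink the subset by an amount that the documents do not allow one to estimate.

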- the time between the fracture occurred and operation or decision making for non-operative therapy

[figure not shown]
Healing and treatment characteristics

- bone healing after 3 months: union or delayed healing
The decision is made based on conventional radiographs including the clinical description of complains.
- weight bearing after 3 months
Is it possible or not?
- hindfoot axis (varus/valgus-deformity, Böhler angle, subtalar osteoarthritis)
The decision is made based on conventional radiographs and a clinical evaluation.
- type of operation (approach, fixation method, graft)

Complications

- infection (I)
- deep venous thrombosis (DVT)
- nerve paresis/palsy/disturbed sensibility (N)
- subtalar posttraumatic osteoarthritis (PTOA)
- subtalar instability (SI)
- local mechanical irritation by plate/screws (LI)
- wound irritations (WI) as superficial healing problems or skin edge necrosis
- irritations associated to the use of the custom-made heel-unloading orthosis ('Settner shoe')

Participant timeline

The clinical and radiological controls correlate with the usual guidelines for treating calcaneus fractures at the Odense University Hospital.

Sample size and power analysis

The sample size calculation was based on a 33% difference in activity, correlating with a clinical relevant difference. Setting the power to 80% and the 2-sided confidence interval to 95% the calculation according to the method of Fleiss with continuity correction resulted in 25 patients per group.

Recruitment

All consultants of the trauma section of the Department of Orthopaedics and Traumatology at the University Hospital Odense are involved in the recruitment process of the study.

Methods: Assignment of interventions (for controlled trials)

Allocation

In the period between treatment (either decision-making for non-operative therapy or open reduction and internal fixation) and consolidation of the soft-tissue situation, the patients are randomized for the aftercare with or without the custom-made heel-unloading orthosis ('Settner shoe'). As soon as the soft-tissue situation allows the adjustment, the patients are referred to an orthopaedic shoemaker, who equips the patient accordingly. The randomization is done using the tool provided by OPEN.

Blinding (masking)

The allocation is not blinded, because it will be obvious to the patient, whether a special shoe is worn or not. Furthermore, the treating trauma surgeon needs to initiate the prescription.

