Measurement of physical activity

For monitoring of activity, the patients are equipped with a Misfit™ Shine (Burlingame, CA, USA) at the ankle and an Axivity™ AX3 (Newcastle upon Tyne, UK) at the lateral femur of the unaffected side. If there is a fracture at both sides, the trackers are attached to the side with the less complicated fracture. The wear time is 7 days. At day 7±14 (discharge) and after 3±0.5 months patients are equipped, and activity signals are analyzed by calculating the mean of all acquired 24-hour-data during these two periods. Regarding the Misfit™ Shine, only the number of registered steps is recorded. Regarding the Axivity™ AX3, the portion of highly active periods per day and the number of active minutes, correlating with walking activity, have shown to be most discriminating in the preliminary validation study. Therefore, these parameters are selected. Reliability is checked using a wear-time analysis based on change of signal vector magnitudes and temperature monitoring.

Correlating with these two data points, the EuroQol 5D-3L questionnaire [5] and the AOFAS [6] are monitored.

Classification

Classification of calcaneus fractures according to Sanders

[figure not shown]

Figure 3: Axial load is necessary for calcaneus fractures, which should be treated with a heel-unloading 'Settner shoe'.

[figure not shown]

Figure 4: The fracture classification according to Sanders can group the calcaneus fractures that occur following axial load [7].

Classification of open fractures according to Gustilo-Anderson

| Gustilo Grade | Definition |
|---------------|--|
| I | Open fracture, clean wound, wound <1 cm in length |
| II | Open fracture, wound > 1 cm but < 10 cm in length without extensive soft-tissue damage, flaps, avulsions |
| III | Open fracture with extensive soft-tissue laceration (>10 cm), damage, or loss or an open segmental fracture. This type also includes open fractures caused by farm injuries, fractures requiring vascular repair, or fractures that have been open for 8 hr prior to treatment |
| IIIA | Type III fracture with adequate periosteal coverage of the fracture bone despite the extensive soft-tissue laceration or damage |
| IIIB | Type III fracture with extensive soft-tissue loss and periosteal stripping and bone damage. Usually associated with massive contamination. Will often need further soft-tissue coverage procedure (i.e. free or rotational flap) |

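### Age and Sanders type are known before randomisation, but the primary comparison is unadjusted; pre-specified adjustment would gain precision if these covariates are prognostic

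*Combined protocol and SAP*

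**What the plan says.** Under Outcomes, the primary criterion is numeric: "The number of active minutes per day following 3 months (time point 2) is primary outcome criterion". Under Patient characteristics beside outcome criteria, the plan lists age, sex, "body mass index" and ASA class as epidemiology, and "classification according to Sanders (figure 4" as an injury characteristic. It also lists soft-tissue damage, polytrauma, indication for operation and time from fracture to treatment. The Eligibility criteria require age 18 to 65 and a fracture that can be given a Sanders type. Patients enter after the operation or the non-operative decision, and the Allocation section places randomisation after that point. Age and Sanders type are therefore known before allocation. The plan does not say when body mass index is measured.

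The Statistical methods section names a Student's t-test (written as paired) for normally distributed data. Otherwise, "nonparametric tests as the Mann-Whitney U-test for two and the Kruskal-Wallis H-test for multiple variables determine the significance of difference". Chi-square tests and Spearman correlations complete the list. There is no regression or analysis of covariance, and the Allocation section names no stratification factor.

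**The concern.** The trial has 50 patients and a broad population: ages 18 to 65, all Sanders-classifiable fractures, operated or not. Spread in daily walking between such patients goes wholly into the standard error of an unadjusted comparison. If age, fracture severity or body mass index predicts walking at 3 months, a model containing them would give a narrower interval from the same patients.

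No pre-injury activity measurement is planned. The time point 1 measurement is made around discharge, is itself a secondary outcome, and is not shown to precede allocation, so it cannot safely serve as a baseline. The recorded patient and injury characteristics are what remains for adjustment. If the covariates are not named in advance, adjusting after an imbalance has been seen invites the charge of selection.

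**Working it through.** **1. The plan's own figure.** Sample size and power analysis takes a 33% change in activity as the relevant effect, with 80% power and a two-sided 5% error rate. It reports that "the calculation according to the method of Fleiss with continuity correction resulted in 25 patients per group". Fleiss is a formula for two proportions, and no reference level is given. Trying 67% against 100% (mean 0.835):

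- Uncorrected: n = [1.960·√(2·0.835·0.165) + 0.842·√(0.67·0.33 + 0)]² / 0.33² = 18.6, rounded up to 19.
- Corrected: (18.6/4)·[1 + √(1 + 4/(18.6·0.33))]² = 24.3, rounded up to 25.

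This reproduces 25 per group, but only because of the level chosen; 30% against 63% would give 41. The endpoint is numeric, so 80% is not an established power for the primary comparison. It is used below as an illustrative starting point.

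**2. Starting point as a t-test.** For 25 per group, two-sided 5%, 48 degrees of freedom and 80% power, the noncentral t gives a detectable difference of d = 0.81 SD. The documents give no SD, so this cannot be put into minutes.

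**3. Effect of adjustment.** Let R² be the share of outcome variance explained by q covariates. R² is an assumption. The documents' only pointer to earlier data is that the chosen activity parameters "have shown to be most discriminating in the preliminary validation study", without figures. Estimating the covariates has a cost, so the ratio of adjusted to unadjusted standard error is

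ratio = √[(1 − R²)·(N − 3)/(N − 3 − q)], with N = 50 and 48 − q error degrees of freedom.

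The second factor is the expected inflation from chance imbalance: 47/44 for q = 3. Power comes from the noncentral t with effect d/ratio.

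| Assumed R² | Ratio, q = 3 | 95% CI width | Power, q = 3 | Power, q = 5 |
|---|---|---|---|---|
| 0 | 1.034 | 3–4% wider | 77% | 75% |
| 0.05 | 1.007 | about 1% wider | 79% | 77% |
| 0.10 | 0.980 | about 2% narrower | 81% | 80% |
| 0.20 | 0.924 | about 7% narrower | 86% | 84% |
| 0.30 | 0.865 | about 13% narrower | 90% | 88% |

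Here q = 3 is age, body mass index and Sanders type as one term; q = 5 enters Sanders type as four categories. At R² = 0.20, for example, √(0.80·47/44) = 0.924, equivalent to 25/0.924² = 29 patients per group.

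**4. Break-even.** Adjusted power equals 80% at R² of about 0.04 for two covariates, 0.07 for three and 0.11 for five.

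**5. Why the small-sample terms matter.** Using √(1 − R²) alone would give 84%, 88% and 92% at R² of 0.10, 0.20 and 0.30. At 0.10 that shows a gain of 4 points where about 1 is realistic.

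**The case against.** Randomisation makes an unadjusted comparison of independent groups unbiased, and its standard error already allows for chance imbalance. The documents contain no R², no SD and no statement that age, body mass index or Sanders type predicts active minutes. Below the break-even, adjustment costs power. The choice of these three covariates is also a matter of judgement, since others are recorded. Patients with two-sided fractures can have two Sanders types, and active minutes may be skewed, so a bare linear model is not a complete specification.

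All of this stands, and it rules out three stronger readings that a reader might infer. The first is that precision is certainly being lost; that depends on an R² the documents do not give. The second is that a chance difference in age or severity makes the planned result invalid; it does not. The third is that these three variables are the only recorded predictors; sex, ASA class, soft-tissue damage, polytrauma and time to treatment are recorded too.

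What the objection does not remove is the asymmetry. With three covariates, the worst case is a loss of about 3 points of power; at R² of 0.20 to 0.30 the gain is about 6 to 10 points without another patient. The coding and skewness gaps can be closed in the same text.

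**Conclusion.** The point holds as a matter of efficiency. Age and Sanders type are available before allocation, and the plan uses neither in the primary comparison nor in a stated stratification. Whether adjustment helps depends on R² exceeding about 0.07 with three covariates, or 0.04 with two. Over an assumed range of 0.10 to 0.30, the interval narrows by about 2% to 13% and an illustrative 80% power rises to 81% to 90%. These figures assume all 50 patients are analysed, equal groups and a roughly linear model.

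The planned comparison is sound without adjustment provided that it is run for independent groups. The word paired in the t-test sentence, and the use of a two-proportion formula for a numeric endpoint, are separate matters.

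**What to change.** Add to Statistical methods, in substance:

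- The primary result is the adjusted difference between arms, with 95% confidence interval, from a linear model of active minutes per day at time point 2. The terms are randomised arm, age (continuous), Sanders type in two levels (I/II against III/IV; the more severe side in two-sided fractures) and, if recorded at inclusion, body mass index (continuous).
- If active minutes are skewed, use robust standard errors or a transformation; name which one in advance.
- No variable arising after randomisation enters the model, such as bone healing or weight bearing at 3 months. Time point 1 activity is not used as a covariate.
- The unadjusted independent-groups comparison is reported as supportive.
- The R² assumed when choosing the covariates is stated.

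The data form should also fix the recording of body mass index at inclusion. If that is not possible, drop it and use two covariates. The cost is plan text, one coding rule and two or three of 48 degrees of freedom, with the risk of about 3 points of power (three covariates) if the covariates turn out to explain nothing.

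### The 25 per group and 80% power come from a two-proportion formula, but the primary outcome is a continuous mean of active minutes per day, so the stated power is unsupported

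*Combined protocol and SAP*

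**What the plan says.** All references are to the combined protocol and SAP.

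- **Sample size and power analysis.** "The sample size calculation was based on a 33% difference in activity, correlating with a clinical relevant difference". Power is set at 80% with a two-sided 95% confidence interval, and "the calculation according to the method of Fleiss with continuity correction resulted in 25 patients per group". The section gives no proportions, mean or SD, and does not say which arm's activity the 33% is measured against.
- **Outcomes, Primary outcome criterion.** "The number of active minutes per day following 3 months (time point 2) is primary outcome criterion".
- **Appendices, Measurement of physical activity.** Trackers are worn for 7 days, and "activity signals are analyzed by calculating the mean of all acquired 24-hour-data during these two periods". The accelerometer measures were chosen because they "have shown to be most discriminating in the preliminary validation study". No result of that study is reported.
- **Statistical methods.** "Normally distributed numeric data sets are compared using the paired Student's t-test", with nonparametric tests otherwise. Separately, "Incidences are compared using the chi square test".
- **Trial design.** "The study design is a parallel group, randomized controlled trial with open allocation".

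**The concern.** The Fleiss method with continuity correction sizes a comparison of the share of patients with some characteristic in each of two groups. The correction allows for counts being whole numbers and has no place in a comparison of means. The primary outcome is a number of minutes per patient, nothing in the plan turns it into yes or no, and the plan itself reserves the chi-square test for incidences. The analysis that was sized is therefore not the one that will be run.

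Two proportions fix their own variance, so that formula needs no SD. A comparison of means does need one. The three stated inputs (33%, 80%, 95%) do not determine the power of a comparison of means.

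This paragraph is the only justification of the trial's size. If the result is null, a reader cannot tell whether a 33% difference in active minutes was likely to be detected. The introduction also expects the trial to settle whether the cost of the orthosis is justified, so a null result would carry weight.

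**Working it through.** **1. Inputs**

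- From the sample size section: two-sided alpha 0.05 (z = 1.960), power 0.80 (z = 0.842), a 33% difference and 25 per group.
- Not in the document: the two proportions, the mean and the SD of active minutes, and the reference arm. Values used for these are assumptions.

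**2. Reproducing the 25**

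With p̄ = (p1 + p2)/2 and d = |p1 − p2|:

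- n′ = [1.960·√(2p̄(1−p̄)) + 0.842·√(p1(1−p1) + p2(1−p2))]² / d²
- n = (n′/4)·[1 + √(1 + 4/(n′d))]²

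For 67% v 100%, p̄ = 0.835 and d = 0.33:

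- n′ = (1.029 + 0.396)² / 0.1089 = 18.6
- n = (18.6/4)·(1 + √1.650)² = 24.3, rounded up to 25

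Other pairs 33 points apart:

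| Proportions | n per group | Rounded up |
|---|---|---|
| 0% v 33% | 24.3 | 25 |
| 0.5% v 33.5% | 24.8 | 25 |
| 1% v 34% | 25.3 | 26 |
| 2% v 35% | 26.2 | 27 |
| 60% v 93% | 30.5 | 31 |
| 50% v 83% | 36.7 | 37 |
| 33% v 66% | 40.7 | 41 |

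For a 33-point difference the formula returns 25 only when one proportion is within about 1 percentage point (more exactly 0.7) of 0% or 100%. This suggests that relative activity (one arm at 100%, the other at 67%) was entered as a proportion of patients. That is an inference. The mismatch does not depend on it.

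**3. What 25 per group gives for a difference in means**

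For an unpaired two-sided 5% t-test with n = 25 per arm, there are 48 degrees of freedom and the noncentrality is δ·√(25/2), where δ is the difference divided by the SD. Power reaches 80% at δ = 0.809. The normal approximation, (1.960 + 0.842)·√(2/25), gives 0.792.

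The 33% can be read in two ways:

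- **Reading A, 33% of the lower-arm mean.** 80% power needs an SD of at most 0.33/0.809 = 0.408, or 41% of that mean.
- **Reading B, 33% of the higher-arm mean.** The lower mean is 0.67 of the higher, so the gap is 0.33/0.67 = 49% of the lower mean. 80% power needs an SD of at most 41% of the higher mean, which is 0.4925/0.809 = 0.609, or 61% of the lower mean.

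Power at 25 evaluable per arm, over an assumed range of SDs:

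| SD as % of lower-arm mean | Power, A | Power, B |
|---|---|---|
| 30 | 97% | >99% |
| 40 | 82% | 99% |
| 50 | 63% | 93% |
| 60 | 48% | 81% |
| 80 | 30% | 57% |
| 100 | 21% | 40% |

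The table assumes normal data and the same SD in both arms. At an SD of 60% of the lower-arm mean, the unstated reference arm alone moves power from 48% to 81%.

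**4. Fewer evaluable patients**

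The plan states no allowance for loss. If only 22 or 20 per arm were evaluable (assumed numbers), power at 0.809 SD would be 75% or 70%.

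**The case against.** The best defence is that no loss of power has been shown. If the SD is at most about 41% of the mean that the 33% refers to, 25 evaluable per group is enough. The preliminary validation study may hold an SD that supports this. The formula used for planning also changes neither the eventual estimate nor the type I error. All of this is right, and it is why the conclusion is that the power is unsupported rather than too low. It does not supply the missing justification, because the plan neither reports an SD nor says that one was used.

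One might also look for a proportion that the formula could apply to. The nearest is the portion of highly active periods per day. That is a secondary outcome and a share of time within each patient, not a share of patients.

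Three narrower objections have some force:

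- A sentence giving 80% power for 0.81 SD is worked back from the existing 25, so it does not by itself show that 25 suits a 33% difference. It has to be paired with an SD.
- The t-test figures assume normality and equal SDs. They do not cover the nonparametric test planned for non-normal data.
- The word paired and the allowance for loss are separate matters. The first belongs in the fix because the calculation and the test must agree. Neither is needed for the main point.

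**Conclusion.** The concern holds. The sample size was derived with a method for a different type of outcome, and the 80% power cannot be verified from the plan. What can be said is that 25 evaluable patients per group give 80% power for a difference of 0.81 SD. Whether a 33% difference is that large depends on an SD and a reference arm that the plan does not give, so true power may be above or below 80%. The mismatch itself rests only on the document's text. The range of powers rests on assumed SDs, equal SDs in the two arms and normal data. This should be fixed, because it concerns the only stated basis for the trial's size on its primary comparison.

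**What to change.** Replace the Fleiss sentence in the sample size section with a two-sample means calculation, for example: *With 25 evaluable patients per group, a two-sided 5% unpaired t-test has 80% power for a difference of 0.81 SD in mean active minutes per day at 3 months.* Then:

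1. Express the 33% in minutes per day and name the arm it refers to.
2. Restate the power for that difference with an SD from the preliminary validation study, if it comes from a comparable population and time point. Otherwise give power over a stated SD range. State the equal-SD and normality assumptions.
3. In Statistical methods, change paired to unpaired (independent groups), so that the planned test fits the parallel-group design and the calculation.

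Power at a stated smaller evaluable number can be given alongside.

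The cost is one rewritten paragraph and one corrected word. The correction itself requires no extra enrolment. The restated power may be less favourable, and if it falls below 80% the sponsor should either state that this is accepted or reconsider the number.
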